## PURPOSE OF THE STUDY AND BACKGROUND

---

### Purpose of the Study

The aim of the study is to assess the clinical relevance of 3D stereographic reconstructions (from sterEOS 3D) on patients, adults and children, who undergo spine surgery. This study will observe the value of 3D parameters at three different steps of the standard of care surgical procedure: preoperatively, peri-operatively, and post-operatively. The goal of this prospective study is to observe how 3D reconstructions could enhance the planning, the surgery and the post-op analysis and outcomes. This pilot study could help to understand which and how 3D parameters could improve adult and pediatric spine surgery.

### Background

#### EOS

The biplanar low-dose EOS system and its associated sterEOS workstation (EOS®, EOS Imaging, Paris, France) allows 3D spine reconstructions. The EOS system presents some advantages over MRI or CT Scans. The weight bearing position allows assessment in the functional position and the radiation exposure is 800-1000 times less than CT scans, allowing full spine acquisition even in pediatric patients. Selected anatomical landmarks are utilized to reconstruct a 3D model of the spine allowing global assessment as well as localized analysis.

### Our hypothesis is that:

1. 3D parameters could bring additional information in pre-operative, surgery and post-op control.

## STUDY DESIGN

---

The study will be prospective, randomized, occurring in New-York Presbyterian Hospital. The study design includes 4 arms:

- Cohort A: Adults and standard of care (EOS biplane acquisition). Planning performed with current practice.
- Cohort B: Adults and standard of care (EOS biplane acquisition). Planning performed with additional 3D information provided by 3D modeling on sterEOS software (FDA approved)
- Cohort C: Children and standard of care (EOS biplane acquisition). Planning performed with current practice.
- Cohort D: Children and standard of care (EOS biplane acquisition). Planning performed with additional 3D information provided by 3D modeling on sterEOS software (FDA approved)

For cohort B and D, 3D additional information will be provided to the surgeons. This information may help them to better understand the pathology and plan the procedure.

Radiographic, clinical parameters and freeform observations by the surgeon will be collected at pre-operative, peri-operative and post-operative steps, for patients who meet the inclusion criteria and signed the informed consent. The recorded parameters and freeform observations will be compared between patients of cohort A and B, and cohort C and D.

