### Number of Subjects

Every patient with spinal deformity meeting the inclusion criteria will be enrolled in this prospective pilot study. Around 160 subjects are anticipated to enroll in the project. Patients with spinal deformity will be identified during office hours of [name] for adults and pediatrics, [name] for Adults and pediatrics, and [name], [name] and [name] for pediatrics. Patient will be segregated between the different cohort regarding their age (A and B for adults, C and D for children).

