## **Data Analysis and Data Monitoring**

This pilot study is mainly an observational study. The aim of the study is only to observe the value of additional information provided by 3D modeling with sterEOS software.

At the end of the 6 first months of the study, a first data analysis will be performed at Columbia with the available data in order to have some preliminary results. The final data analysis will be performed at the end of the data collection, when every patients enrolled will have the full assessment (preop, periop and post-op data). This analysis will be performed at EOS Imaging with the shared data provided by Columbia.

Descriptive analysis (mean, range and standard deviations) will be calculated for all the parameters and HRQOL data with Excel software. Correlations will be performed using Pearson correlation coefficient, and Student's t-Test will be utilized to determine if these correlations are significant, with significant p-value set at 0.05.

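### One question about 3D planning is answered by two separate age-group contrasts, with no age-stratified overall estimate and no arm-by-age comparison

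*Combined protocol and SAP*

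**What the plan says.** The hypothesis is a single statement, not divided by age: "3D parameters could bring additional information in pre-operative, surgery and post-op control". Purpose of the Study likewise applies the aim to adults and children together.

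STUDY DESIGN describes four arms. A and B are adults planned without and with the added sterEOS 3D information; C and D are the same pair for children. Its opening line is "The study will be prospective, randomized, occurring in New-York Presbyterian Hospital", and the comparison it plans is "The recorded parameters and freeform observations will be compared between patients of cohort A and B, and cohort C and D".

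On size, Number of Subjects says "Around 160 subjects are anticipated to enroll in the project". It gives no derivation, no adult/child split and no allocation ratio. Age decides which pair of cohorts a patient enters.

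Data Analysis and Data Monitoring lists descriptive statistics and Pearson correlations. On testing it says "Student's t-Test will be utilized to determine if these correlations are significant", "with significant p-value set at 0.05". It specifies no between-cohort test or model, no combined estimate, no arm-by-age comparison and no primary endpoint. The same section says "This pilot study is mainly an observational study".

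**The concern.** B against A and D against C contrast the same change in planning. The Data Collection tables are organised by planning arm, not by age, with the same instruments and films at the same visits. Age group is therefore a stratum. The two within-age differences can be averaged without ever comparing an adult with a child.

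Without that average, the study gives two imprecise answers to one question and leaves the more precise one uncomputed. Without an arm-by-age comparison, it also has no planned way to read two results that differ. The foreseeable misreading is that 3D planning helps only the age group in which the difference looks clear, when chance alone often produces that pattern.

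**Working it through.** There is no sample-size figure to reproduce: the 160 comes with no effect size, SD, power or precision target. What follows is an illustration.

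**Inputs**
- Total of about 160: Number of Subjects.
- 1:1 allocation within age group and an 80/80 age split, so n = 40 per cohort: assumed. A 40/120 split is shown as the range.
- Continuous outcome with SD 1 and the same true effect d (in SD units) in both age groups: assumed.
- Two-sided 0.05 applied to the cohort contrasts: assumed. It is needed only from step 2 on.

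**1. Precision (needs no test)**
- Separate contrast: SE = √(2/40) = 0.224, so the 95% half-width is 1.96 × 0.224 = 0.44 SD.
- Stratified (inverse-variance) estimate: SE = 1/√(1/0.05 + 1/0.05) = √0.025 = 0.158, so the half-width is 0.31 SD.
- Ratio 0.158/0.224 = 0.707, an interval 29% shorter.
- With a 40/120 split (20 and 60 per cohort) the separate SEs are √(2/20) = 0.316 and √(2/60) = 0.183. The stratified SE is 1/√(10 + 30) = 0.158, unchanged.

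**2. Chance disagreement under one common effect (normal approximation)**
- Power per contrast: p = Φ(d/0.224 − 1.96); the wrong-direction tail is negligible.
- Exactly one contrast significant: 2p(1 − p).
- Estimates with opposite signs: 2q(1 − q), with q = Φ(−d/0.224).

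| d | Power, each contrast | Power, stratified | Exactly one significant | Opposite signs |
|---|---|---|---|---|
| 0.2 | 14% | 24% | 25% | 30% |
| 0.3 | 27% | 48% | 39% | 16% |
| 0.4 | 43% | 72% | 49% | 7% |
| 0.5 | 61% | 88% | 48% | 2.5% |
| 0.6 | 76% | 97% | 36% | 0.7% |

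With equal cohorts, 2p(1 − p) cannot exceed 50%. With a 40/120 split, discordant significance reaches 58% at d = 0.5, and opposite signs occur in 11% of trials at 0.4 and 6% at 0.5. Significant results in opposite directions occur in about 0.1% of trials or fewer throughout.

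**3. Can the trial tell chance from a real age difference?**
- SE of the difference between the two contrasts: √(4/40) = 0.316.
- Difference detectable with 80% power: (1.96 + 0.842) × 0.316 = 0.89 SD.

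Only a very large age difference would be identified reliably, so a rule for reading two differing results has to be set in advance.

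**The case against.** The strongest reply is that this is a pilot with a mainly observational aim, and that separate reporting by age is sensible. Adults and children have separate eligibility sections, and some surgeons recruit only paediatric patients. That stands: the age-specific estimates should be kept, and a mixed average need not decide anything. It is no reason to leave out the stratified estimate, because a small study has the most to gain from using all its patients.

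It can also be said that the hypothesis concerns additional information, which the 2D and 3D planning questionnaires, both completed in the 3D cohorts, could address within patients. That is fair, but STUDY DESIGN still commits to the between-cohort comparisons.

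Four stronger readings are tempting, and the documents do not support them:
- **That the two contrasts will easily give opposite answers.** The 48–49% at 0.4–0.5 SD is the chance that one is significant and the other is not. Opposite signs occur in only about 2.5–7% of trials there, and are common only for small effects.
- **That a split result is what chance should be expected to produce.** It is common, at about 25–50%, but with equal cohorts it is never more likely than not.
- **That the plan nearly doubles its false-positive rate.** Two independent tests give 1 − 0.95² = 9.75%, but only if both contrasts are tested at 0.05 and either one counts as support. The plan attaches 0.05 to correlations and states no such rule.
- **That the combined contrast should be decisive for every outcome.** With no primary endpoint among many radiographic parameters and five quality-of-life instruments, that label would decide nothing and would control no error rate.

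**Conclusion.** The point holds as a loss of precision and a gap in interpretation. One hypothesis is met by two partial estimates, with no age-stratified summary and no arm-by-age comparison. With 40 per cohort, the stratified estimate cuts the standard error from 0.224 to 0.158 SD. That gain depends on assumed cohort sizes, 1:1 allocation within age and a common SD, but on no hypothesis test. The 25–50% chance of a split result is more conditional: it also assumes testing at two-sided 0.05 and the same true effect of 0.2 to 0.6 SD in both age groups. This does not invalidate an observational pilot; it is a specific improvement that costs little.

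**What to change.** In STUDY DESIGN and in Data Analysis and Data Monitoring, for outcomes recorded in all four cohorts and comparable across ages:

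1. Add an age-stratified estimate of 3D against current-practice planning, from a linear model with planning arm (B and D against A and C) and age group, with a 95% interval.
2. Show it beside the A–B and C–D estimates, each with its own interval. Outcomes not comparable across ages stay age-specific.
3. Claim that the effect differs by age only from the arm-by-age-group interaction estimate and its interval, never because one contrast is significant and the other is not.
4. Label all of this exploratory.

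The cost is a few sentences and a simple model, with no new patients, visits or data. The downside is that the overall estimate averages adult and paediatric deformity, so it must not appear without the age-specific ones.

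Stratifying does not remove the bias from the note under the children's EOS exclusion criteria, which moves patients who meet only those criteria into A or C. Those patients should be left out of the randomized comparison, with the criteria applied in the same way to both planning arms and preferably before allocation. Otherwise the shorter interval surrounds an estimate that still carries that selection.

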### Number of Subjects

Every patient with spinal deformity meeting the inclusion criteria will be enrolled in this prospective pilot study. Around 160 subjects are anticipated to enroll in the project. Patients with spinal deformity will be identified during office hours of [name] for adults and pediatrics, [name] for Adults and pediatrics, and [name], [name] and [name] for pediatrics. Patient will be segregated between the different cohort regarding their age (A and B for adults, C and D for children).

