#### **EOS exclusion Criteria:**

- Patients younger than 7 years old
- Patients with supernumerary vertebrae (one extra or one less thoracic or lumbar vertebrae)
- Patients with hemivertebrae
- Insufficient quality of images to perform the 3D modeling with sterEOS software

**Note:** Every patient who only meets the EOS exclusion criteria will be automatically transferred in the A cohort if they are over 18, and in the C cohort if they are younger than 18 years old.

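### Surgeon is used in neither the stated allocation nor the analysis, although surgeons receive the 3D information and their observations are compared between cohorts

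*Combined protocol and SAP*

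**What the plan says.** - **Design.** Study Design states: "The study will be prospective, randomized". It gives no method, ratio, strata or concealment. It plans to compare recorded parameters and surgeons' observations between A and B, and between C and D.
- **Sorting by age.** Number of Subjects states: "Patient will be segregated between the different cohort regarding their age (A and B for adults, C and D for children".
- **Sorting by image criteria.** The note closing the EOS exclusion criteria for children states: "Every patient who only meets the EOS exclusion criteria will be automatically transferred in the A cohort if they are over 18". Those under 18 go to C.
- **Recruitment.** Number of Subjects states: "Patients with spinal deformity will be identified during office hours". It lists five clinicians, two seeing adults and children and three seeing children only. On size it states: "Around 160 subjects are anticipated to enroll in the project".
- **The surgeon's part.** Study Design gives the 3D information to the surgeons in B and D. On data it states: "freeform observations by the surgeon will be collected", at the pre-, peri- and post-operative steps.
- **Analysis.** Data Analysis and Data Monitoring lists descriptive statistics, Pearson correlations and a t-test of those correlations at 0.05. It has no surgeon term and names no test for the between-cohort comparisons.

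**The concern.** The intervention is information handed to a surgeon, who then plans and operates and supplies part of the data being compared. Reporting style, case mix and technique can all differ between surgeons. The surgeon is normally known when the patient enrols, so the factor could be balanced in advance or adjusted for later. The plan states neither.

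If one surgeon's patients fall mainly in one cohort, a difference between surgeons is mixed with the difference between planning methods in that trial. Even without imbalance, leaving surgeon out of the comparison puts between-surgeon variation into the error term, which matters when cohorts are small.

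**Working it through.** **Inputs.** From the documents: about 160 patients, four cohorts, and five recruiting clinicians (two for A/B, five for C/D). Assumed, because the documents give no figures: equal cohorts (160/4 = 40), recruiting clinicians who are the operating surgeons, equal caseloads (80/5 = 16 children and 80/2 = 40 adults per surgeon), simple 1:1 randomisation, and between-surgeon differences of 0.5, 1.0 or 1.5 within-surgeon SD. The 160 cannot be reproduced, since no effect size, SD or power is stated.

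**1. How often a surgeon is split unevenly** (binomial, two-sided, surgeons independent)
- Children, 12:4 or worse: 2 × 2517/65536 = 0.0768; any of five: 1 − (1 − 0.0768)^5 = 0.329.
- Children, 13:3 or worse: 0.0213; any of five: 0.102.
- Adults, 26:14 or worse: 0.0807; any of two: 1 − (1 − 0.0807)^2 = 0.155.

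**2. How often surgeon mix differs between cohorts** (simulation). A split alone is not confounding; what matters is the gap between a surgeon's shares of the two cohorts.
- Adults, two surgeons: a gap of 20 points or more in 9% of trials at 40 per cohort (7% with a 70:30 caseload), and 27% at 20 per cohort.
- Children, five surgeons: at least one gap of 20 points or more in 16% at 40 per cohort, and about 54% at 20 per cohort.

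**3. How far the estimate moves.** Shift = gap in shares × surgeon difference.
- A 20-point gap gives 0.2 × 0.5, 1.0 or 1.5 = 0.10, 0.20 or 0.30 SD.
- One paediatric surgeon at 12:4 with the other four at 8:8 has shares 12/44 and 4/36, a gap of 0.16. If that surgeon differs from the rest by 1 SD, the shift is 0.16 SD.
- For scale, the standard error at 40 v 40 is √(2/40) = 0.22 SD.

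**4. False positives of an unadjusted two-sample t-test with no 3D effect** (simulation, two surgeons, 40 per cohort)
- Over all trials: about 5% for each surgeon difference.
- Within trials with a gap of 20 points or more: about 8%, 13% and 19% for 0.5, 1.0 and 1.5 SD.

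**5. Precision lost by ignoring surgeon.** With two equal surgeons differing by d, the total SD is √(1 + d²/4): 1.03, 1.12 and 1.25 for d = 0.5, 1.0 and 1.5. The unadjusted standard error is therefore about 3%, 12% or 25% larger than one based on within-surgeon variation.

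**6. What adjustment costs under imbalance.** Information per surgeon is n1·n2/(n1 + n2).
- Children, balanced: 5 × (8·8/16) = 20. One surgeon at 12:4: 3 + 16 = 19, so the standard error rises by √(20/19) − 1 = 2.6%.
- One surgeon at 13:3: 2.44 + 16 = 18.44, a rise of about 4%.
- Adults, balanced: 2 × 10 = 20. One surgeon at 26:14: 9.1 + 10 = 19.1, a rise of about 2.3%.

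**The case against.** The strongest reply is that the age sentence only sorts patients into A/B or C/D. It does not say how A is separated from B, so stratification by surgeon is unstated rather than rejected. That stands, and if it is intended, writing it down settles the allocation half of the point. The analysis half remains.

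A second reply is that the study is a pilot described as mainly observational. Patients in B and D are also scheduled for both a 2D and a 3D planning questionnaire before surgery, and a within-patient contrast of these would largely cancel differences between surgeons. This lowers the stakes. It does not remove them, because Study Design still plans the between-cohort comparisons.

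Third, blocking by surgeon has a price. Surgeons see the allocation and could follow their own sequence within up to seven strata (two adult, five paediatric). That is a fair cost.

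A reader might infer three stronger things that do not hold:
- *That the omission inflates the false-positive rate.* It does not under true randomisation; step 4 gives about 5% overall. The 8–19% figures apply only to the imbalanced minority of trials and to assumed surgeon effects.
- *That adjustment cannot rescue an imbalanced trial of this size.* Step 6 shows that it recovers nearly all the information.
- *That surgeons complete all the questionnaires.* Data Collection does not say who completes the planning, surgical and post-operative forms. Only the freeform observations are expressly the surgeon's, and quality of life and pain are self-reported.

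Nor is age the sole rule that fixes a cohort, since the EOS transfer does so too; that rule ignores surgeon and so does not answer the point.

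**Conclusion.** The point holds as a cheap improvement, of minor severity. Surgeon enters neither the stated allocation nor the stated analysis, in a design where surgeons use the intervention and supply part of the compared data. The harm is possible bias in a particular unlucky trial and some loss of precision, not an invalid test. Under the stated assumptions, at least one of five paediatric surgeons is split 12:4 or worse in about 33% of trials, but the resulting shift for a 1 SD surgeon difference (0.16 SD) is smaller than the standard error (0.22 SD). The documents give no cohort sizes, caseloads or surgeon-effect sizes. Smaller cohorts would make imbalance more common, and small surgeon effects would make it unimportant.

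**What to change.** 1. **Analysis (the main change).** Record the surgeon for every patient and include surgeon as a factor in the A v B and C v D comparisons. This costs one sentence and a few degrees of freedom: one for the two adult surgeons, four for the five paediatric surgeons.
2. **Allocation (preferable).** State that A v B and C v D are randomised 1:1 within surgeon and age group, from a computer-generated list with randomly varying block sizes, concealed and held by someone other than the surgeons. This costs one paragraph and a stratified list, with no extra patients. The downside is some predictability within blocks, because surgeons are not blind to allocation; varying the block size limits it.
3. **Timing.** Issue the allocation only after eligibility and EOS image suitability are confirmed, and reword the transfer note so that patients failing only the EOS criteria stay outside the randomised comparison. Otherwise that note places patients in A or C non-randomly, whatever is done about surgeon.

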### Age and Gender of Subjects

Both male and female patients will be included in the study. Regarding the age, the study will include every patient without age limit.

### Racial and Ethnic Origin

For the enrollment of this study, there are no racial restrictions.

### Estimated Duration of Study:

2 years (study end planned for July 2018)

## **Human Subject (Inclusion/Exclusion Criteria):**

### **Adults:**

#### **Inclusion Criteria:**

- All patients must be age 18 or greater at the time of surgery or initial consultation
- Having a primary surgery of their spine (Fusion or instrumentation)

#### **Exclusion Criteria:**

- Diagnosis of scoliosis other than degenerative or idiopathic (i.e. paralytic/neuromuscular, congenital)
- Undergoing revision (Fusion / Instrumentation)

#### **EOS exclusion Criteria:**

- Patients with supernumerary vertebrae (one extra or one less thoracic or lumbar vertebrae)
- Patients with hemivertebrae
- Insufficient quality of images to perform the 3D modeling with sterEOS software

### **Children:**

#### **Inclusion Criteria:**

- All patients must be younger than 18 at the time of surgery
- Having a primary surgery of their spine (Fusion or instrumentation)

#### **Exclusion Criteria:**

- Diagnosis of scoliosis other than degenerative or idiopathic (i.e. paralytic/neuromuscular, congenital)
- Undergoing revision (Fusion / Instrumentation)

#### **EOS exclusion Criteria:**

- Patients younger than 7 years old
- Patients with supernumerary vertebrae (one extra or one less thoracic or lumbar vertebrae)
- Patients with hemivertebrae
- Insufficient quality of images to perform the 3D modeling with sterEOS software

**Note:** Every patient who only meets the EOS exclusion criteria will be automatically transferred in the A cohort if they are over 18, and in the C cohort if they are younger than 18 years old.

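### Patients who meet only the EOS exclusion criteria all go to control cohorts A or C, so A versus B and C versus D do not compare like groups

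*Combined protocol and SAP*

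**What the plan says.** *Study Design* states: "The study will be prospective, randomized". It defines cohorts A and B for adults and C and D for children, with 3D information given to the surgeons in B and D only. It adds: "The recorded parameters and freeform observations will be compared between patients of cohort A and B, and cohort C and D".

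General and EOS-specific exclusions are listed separately. For all ages, the EOS list covers one vertebra too many or too few, hemivertebrae, and "Insufficient quality of images to perform the 3D modeling with sterEOS software". For children it adds "Patients younger than 7 years old".

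Meeting only an EOS criterion does not keep a patient out of the study. The Note after the children's list says: "Every patient who only meets the EOS exclusion criteria will be automatically transferred in the A cohort if they are over 18". It sends children to C. It covers both age groups and names only A and C as destinations.

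*Age and Gender of Subjects* says "the study will include every patient without age limit", so a child under 7 can be enrolled, but only in C.

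The documents do not say whether the EOS criteria are applied before or after randomisation, and they give no allocation ratio. *Data Analysis and Data Monitoring* defines no analysis set, no flag for transferred patients and no adjustment.

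**The concern.** Randomisation makes A and B (and C and D) alike in everything except the 3D information. The Note undoes this by tying vertebral anatomy, image quality and, in children, age to the cohort. Each of these could plausibly affect surgical planning, the operation, or the radiographic and quality-of-life results. A difference between cohorts could then partly reflect who was moved. A larger sample does not reduce this bias. Without a flag on transferred patients, it may not be possible to remove it at analysis.

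The harm is confined to the between-cohort comparisons. Comparing the 2D and 3D planning questionnaires within patients of B and D, both of which the *Data Collection* schedule marks there, is unaffected.

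**Working it through.** The plan gives no figure to reproduce. The check takes the two possible timings in turn and then the size.

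**Inputs.** From *Number of Subjects*: "Around 160 subjects are anticipated to enroll in the project". Assumed, because the documents are silent:
- 80 patients per age group, allocated 1:1, so n = 40 per cohort before transfer;
- a share p of patients who meet only EOS criteria;
- a mean difference of d SD on the outcome between ineligible and eligible patients, with unit SD within each group;
- no true effect of the 3D information;
- analysis in the cohort the patient ends up in.

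**Transfer before randomisation.** The 80p ineligible patients go straight to control and the other 80(1−p) are split equally. The 3D cohort has 40(1−p) and control has 40(1−p) + 80p = 40(1+p). All ineligible controls are non-randomised.

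**Transfer after randomisation.** Each cohort of 40 contains 40p ineligible patients. Control keeps its own and receives those from the 3D cohort, giving 40(1+p) and 40(1−p). About half the ineligible controls were randomised there and half were moved in.

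Both timings give the same expected result: an ineligible share s = 80p / [40(1+p)] = 2p/(1+p) in control and 0 in the 3D cohort. A simulation of 80 patients per age group (40,000 runs) agrees. The mean control share for transfer after versus before randomisation was 9.5% v 9.4% at p = 5%, 18.0% v 18.0% at 10%, and 33.2% v 33.1% at 20%.

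**Size.** Bias in the difference in means = s × d. Its standard error is √{[1 + s(1−s)d²]/[n(1+p)] + 1/[n(1−p)]}.

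For p = 10%, d = 0.5: s = 0.2/1.1 = 0.182; bias = 0.182 × 0.5 = 0.091; SE = √(1.037/44 + 1/36) = 0.227; ratio = 0.40.

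| p | Control (ineligible) v 3D | s | Bias in SD, d = 0.5 (bias/SE) | Bias in SD, d = 1 (bias/SE) |
|---|---|---|---|---|
| 2% | 40.8 (1.6) v 39.2 | 3.9% | 0.02 (0.1) | 0.04 (0.2) |
| 5% | 42 (4) v 38 | 9.5% | 0.05 (0.2) | 0.10 (0.4) |
| 10% | 44 (8) v 36 | 18.2% | 0.09 (0.4) | 0.18 (0.8) |
| 20% | 48 (16) v 32 | 33.3% | 0.17 (0.7) | 0.33 (1.4) |

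The shares and the bias in SD do not depend on n; the ratio to the standard error does.

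**If a test were used.** The plan specifies no between-cohort test. As an illustration, a two-sided t-test at 0.05 with no true effect would reject in about 5.5%, 6.6% and 10% of trials at p = 5%, 10% and 20% with d = 0.5, and in about 6.5%, 11% and 26% with d = 1. Limiting both cohorts to eligible patients returned the rate to about 5%.

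**The case against.** The best defence has four parts.

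1. *Stakes.* The plan calls this a pilot that is mainly observational. It specifies descriptive statistics and correlations, and gives the between-cohort comparison no confirmatory role. That lowers the stakes. But the comparison is planned, and descriptive means carry the same bias as tested ones.

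2. *Size.* Neither p nor d is documented. Congenital scoliosis is already a general exclusion, which may remove many hemivertebra cases, and the age criterion applies only to children. At p = 2% to 5% the bias is at most 0.10 SD, or 0.4 of a standard error. This stands: the imbalance is certain in direction but may be small, and the 20% row is an upper illustration.

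3. *Analysis by original assignment.* If transfer followed randomisation and patients were analysed as first assigned, the comparison would be protected. That is correct in principle, but the plan does not say so. A rule that transfers patients into a cohort, followed by comparison by cohort, reads the other way.

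4. *Image failures.* They may come to light mainly in B and D, because the *Data Collection* schedule marks 3D modelling only there. This is uncertain, since *Radiographic data* does not limit reconstruction to those cohorts. The finding does not depend on it: if failures leave B or D, similar patients remain in A or C.

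**Conclusion.** The concern holds. As written, the Note puts patients who meet only EOS criteria into A or C and never into B or D, and nothing in the analysis section corrects for it. The make-up of the cohorts differs by design whichever way the timing is read, given analysis by final cohort. The size of the resulting bias rests on assumed p and d: from 0.02 SD (p = 2%, d = 0.5) to 0.33 SD (p = 20%, d = 1), with the lower values perhaps more realistic. If d = 0 the means are unbiased, but the cohorts still differ in make-up and size. The rule should be changed because it defeats the purpose of randomising and is cheap to correct.

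**What to change.** - Delete the automatic transfer. Apply the EOS criteria to all patients before randomisation, judging image quality in the same way for everyone on the pre-operative EOS films that every cohort already has. Randomise only those who pass.
- If EOS-ineligible patients are still enrolled, flag them and report them as a separate non-randomised descriptive group, outside A versus B and C versus D.
- If inadequate images are found only after assignment, analyse the patient in the assigned cohort.
- Do not drop such patients from B and D alone. Similar patients would stay in A and C, where the ineligible share would be p and the bias p × d: at p = 10%, 0.05 SD for d = 0.5 and 0.10 SD for d = 1.

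**Cost.** A wording change and an image check at screening. If the check needs a modelling attempt, that is up to about 80 reconstructions (the future A and C patients) beyond those the *Data Collection* schedule marks; reporting flagged patients separately does not in itself need them.

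Precision falls slightly if ineligible patients are not replaced. At p = 10% the comparison is 36 v 36 instead of 44 v 36, and the confidence interval widens by √(2/36) / √(1/44 + 1/36) = 1.049, about 5%. At p = 5% it is 38 v 38 instead of 42 v 38, about 2.5% wider. The enrolment figure is only approximate, so replacement may be possible.

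Keeping late image failures in their assigned cohort dilutes the estimated effect by the share who received no 3D information.
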